5.1.3.1 Prior therapies date imputation

See Section 5.1.3.

5.1.3.2 Post therapies date imputation

See Section 5.1.3.

5.1.4 Other imputations

Only PASI based response variables are imputed with multiple imputation or non-response, other response variables (e.g. DLQI 0 or 1 achievement) will be imputed with LOCF.

5.2 AEs coding/grading

Adverse events will also be coded according to MedDRA dictionary, using a narrow search. The MedDRA version used for reporting the adverse events will be described in a footnote.

Safety topics of interest, such as risks defined in the Safety Profiling Plan, Risk Management Plan or topics of interest regarding signal detection or routine analysis are defined in the Program Case Retrieval Sheet that is stored in at the path

5.3 Laboratory parameters derivations

See Section 2.8.3.

5.4 Statistical models

5.4.1 Primary analysis

No formal hypothesis will be tested.

Treatment difference will be calculated in terms of proportion of response along with 95% CI using normal approximation of binomial distribution.

Sample SAS code:

Novartis For business use only Page 34 SAP 0

Sensitivity analysis:

Sample SAS Code:

Logistic regression model with treatment and body weight (<90 kg, >=90 kg) as explanatory variables.

```
proc logistic data=xxx descending;
  class treatment weight/ param=glm ;
  model <response var> =treatment weight;
  contrast 'trtA vs. trtB ' treatment 1 -1 ;
  run;
```

Logistic regression model with treatment and body weight (<90 kg, >=90 kg) and treatment-by-body weight(<90kg, >=90kg) as explanatory variables.

```
proc logistic data=xxx descending;
  class treatment weight/ param=glm ;
  model <response var> =treatment weight treatment*weight;
  contrast 'A vs B in wgt=1 (<90)' treatment 1 -1 treatment*wgt 1 0 -1 0
/estimate=exp;
  contrast 'A vs B in wgt=1 (>=90)' treatment 1 -1 treatment*wgt 0 1 0 -1
/estimate=exp;
run;
```

Note: 'descending' option is used if Yes is coded as 1 and No is coded as 0

if Yes is coded as 1 and No is coded as 2 then no option is requesired

5.5 Rule of exclusion criteria of analysis sets

Table 5-1 Protocol deviations that cause patients to be excluded

Deviation ID	Description of Deviation	Exclusion in Analyses	Severity code
INCL01	Informed Consent not signed	Excluded from FAS and SAF	3
INCL02	Age criteria not met	Excluded from none of the analysis set	0
INCL03	Diagnosis of chronic plaque type psoriasis is within 6 months prior to Randomization	Excluded from none of the analysis set	0
INCL04	BSA is below 10% and PASI total score is below 12 at visit 2	Excluded from none of the analysis set	0
INCL05	Subject with systemic therapy are not Inadequately controlled by topical Treatment and/or phototherapy and/or previous systemic therapy	Excluded from none of the analysis set	0

Deviation ID	Description of Deviation	Exclusion in Analyses	Severity code
	Having	Excluded from none of	0
EXCL01	psoriasis other than chronic plaque type psoriasis.	the analysis set	
	Medication	Excluded from none of	0
EXCL02	induced psoriasis or medication exacerbation psoriasis	the analysis set	
	Previous	Excluded from none of	0
EXCL03	exposure to secukinumab or any other biologic drug directly targeting IL-17A or IL-17RA receptors.	the analysis set	
	Diagnosis of	Excluded from none of	0
EXCL04	other active ongoing skin diseases or		U
LXOLO4	skin infections (bacterial, fungal, or viral), or inflammatory diseases other than psoriasis that may interfere with the evaluation of psoriasis	the analysis set	
	Ongoing use of	Excluded from none of	0
EXCL05	treatments prohibited by the protocol		· ·
LACEUS	Subjects with	the analysis set Excluded from none of	0
EXCL06	live vaccination within 6 weeks prior to		0
EXCLU6	randomization or any time during the study	the analysis set	
	Use of any	Excluded from none of	0
EXCL07	investigational treatment within 4 weeks prior to Randomization, or within a period of 5 half- lives of the investigational treatment prior to Randomization, whichever is longer.	the analysis set	
	Currently	Excluded from none of	0
EXCL08	enrolled in any other clinical trial involving any investigational agent or device	the analysis set	•
	Patients using	Excluded from none of	0
EXCL09	cholesterol lowering medication who have not been on a stable dose for at least 90 days prior to randomization and who are unable to remain on a stable dose during the study.	the analysis set	
	Pregnant or	Excluded from none of	0
EXCL10	nursing (lactating) women	the analysis set	
	Women of	Excluded from none of	0
EXCL11	child-bearing potential not using effective methods of contraception during dosing of study treatment and for 16 weeks after stopping of study treatment.	the analysis set	-
	Current severe	Excluded from none of	0
EXCL12	progressive or uncontrolled disease which in the judgment of the investigator renders the patient unsuitable for the trial or puts the	the analysis set	

Deviation ID	Description of Deviation	Exclusion in Analyses	Severity code
	patient at increased risk.		
	Underlying	Excluded from none of	0
EXCL13	condition which, in the opinion of the investigator, significantly immunocompro mised the patient and/or places the patient at unacceptable risk for	the analysis set	
	receiving an immunomodula tory therapy.		
	Subject	Excluded from none of	0
EXCL14A	randomized with signs of uncontrolled hypertension (greater than 180 systolic mmHg and Diastolic Blood pressure is greater than 95)	the analysis set	
	Presence of	Excluded from none of	0
EXCL14B	significant medical problems	the analysis set	
	Serum	Excluded from none of	0
EXCL15	creatinine levels are greater than 2.0mg/dL or fasting blood glucose level is greater than or equal to 150mg/dL at screening or hemoglobin A1c greater than or equal to 7% at screening.	the analysis set	
		Excluded from none of	0
EXCL16	Total white blood cells count less than 2500 /ul or thrombocytes less than 1,00,000 /ul or neutrophils less than 1500 /ul or hemoglobin less than 8.5 g/dL at screening.	the analysis set	·
		Excluded from none of	0
EXCL17	Active systemic infections (other than common cold) during the two weeks before randomization	the analysis set	
		Excluded from none of	0
EXCL18	History of active tuberculosis/lat ent tuberculosis after the protocol specified time.	the analysis set	
	Positive	Excluded from none of	0
EXCL19	serology for human immunodeficien cy virus (HIV), hepatitis B or C infection at screening	the analysis set	
	History of	Excluded from none of	0
EXCL20	lymphoprolifera tive disease / known malignancy / history of malignancy of any organ system within the past 5 years	the analysis set	
		Excluded from none of	0
		the analysis set	
EXCL21	History or evidence of ongoing alcohol or drug abuse, within the last 6 months prior to Baseline.	the analysis set	
EXCL21	or drug abuse, within the last 6 months	Excluded from none of	0

Deviation ID	Description of Deviation	Exclusion in Analyses	Severity code
	study treatment and/or patients	-	-
	who are allergic to rubber or latex		
	Medical and/or	Excluded from none of	0
EXCL23	psychiatric and/or other condition which would preclude the patient from	the analysis set	
	adhering to/ completing the protocol.		
EXCL24	Patients unable and/or not willing to self- administer secukinumab injections or who have	Excluded from none of the analysis set	0
	no trained caregiver available to administer the injections		
	Results of	Excluded from none of	0
TRT01	serum pregnancy and/or urine pregnancy test is positive. However, medication is given.	the analysis set	V
TRT02	Patient Withdrew consent. However, dose was administered.	Excluded from none of the analysis set	0
		Excluded from none of	0
TRT03	Incorrect, study medication administered	the analysis set	
		Excluded from none of	0
TRT04	incorrect route of administration of study drug at any time during the study, per protocol	the analysis set	
	Les than 2	Excluded from none of	0
TRT05	injections of study drug administered	the analysis set	-
	More than2	Excluded from none of	0
TRT06	injections of study drug administered	the analysis set	v
		Excluded from none of	0
TRT07	Missed Dose	the analysis set	U
	Use of	Excluded from none of	0
COMD01	prohibited treatment at any time during the study after randomization	the analysis set	Ü
	Receipt of a	Excluded from none of	0
COMD02	live virus vaccination during the study	the analysis set	
WITH01	Patients voluntarily withdrew consent. However, still continuing in the study.	Excluded from none of the analysis set	0
	or	Excluded from none of	0
OTH01	PASI assessment not performed	the analysis set	Č
	ICH-GCP non-	Excluded from none of	0
OTH02	compliance of study site in the study	the analysis set	
	Informed	Excluded from none of	0
OTH03	consent or process documentation deficiencies	the analysis set	
	Failure to	Excluded from none of	0
OTH04	perform key study procedures example	the analysis set	
	blood draw, IGA, PASI		

Novartis	For business use only	Page 38
SAP		0

Deviation ID	Description of Deviation	Exclusion in Analyses	Severity code
OTH05	Wrong weight stratification data entered into IRT at randomization visit	Excluded from none of the analysis set	0

Protocol deviations will lead to subject classification into the analysis sets as follows:

Analysis set exclusions based on population codes

Analysis set	Population codes that cause a subject to be excluded
RAN	NA
SAF	2, 3
FAS	1, 3

Population code text

Population Code	Population code text
0	INCLUDE IN EVERYTHING
1	EXCLUDE FROM FULL ANALYSIS SET (FAS)
2	EXCLUDE FROM SAFETY SET (SAF)
3	EXCLUDE FROM FAS AND SAF

Unless otherwise stated, summary tables, figures and listings will be on all subjects included in the analysis set under consideration.

Table 5-2 Subject Classification

Analysis Set	PD ID that cause patients to be excluded	Non-PD criteria that cause patients to be excluded
RAN	NA	Not randomized
FAS	NA	Not in RAN;
		Mistakenly randomized and no double-blind study drug taken
SAF	NA	No double-blind study drug taken

Page 40

Reference

Julious, S. and Patterson, S. (2004). Sample sizes for estimation in clinical research. Pharmaceut. Statist., 3(3), pp.213-215.

Kianifard, F. and Islam, M. (2011). A guide to the design and analysis of small clinical studies. Pharmaceut. Statist., 10(4), pp.363-368.

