## 5.5.8 Prohibited medication

Use of the treatments displayed in Table 5-2 is NOT allowed for any indication after the start of study treatment; the use of these treatments could confound the efficacy of the study drug. Wash-out periods for these treatments are provided in Table 5-2. If the use of any of these treatments is required, then the patient must NOT be randomized into the study.

The investigator/qualified site staff must instruct the patient to notify them about any new treatments he/she initiates during the study. All prohibited medications and significant non-drug therapies administered after the patient starts study treatment must be listed on the eCRF.

If a prohibited treatment listed in Table 5-2 is used after the start of study treatment, the patient must discontinue use of the prohibited treatment if he/she wishes to continue in the study.

If, in the investigator's clinical judgment, the patient's use of a prohibited treatment presents an undue safety risk for the patient, the patient **must** discontinue study treatment; if a

patient receives a live virus vaccination during the study, the patient **must** discontinue study treatment (see Section 5.6.2).

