#### Table 5-2Prohibited treatment

Prior Therapy (Before Visit 2/Baseline)	
Prohibited Treatments 	Washout Period (before Randomization)
Secukinumab	No prior use allowed
Any biologic drug directly targeting IL-17 or the IL-17 receptor (e.g., ixekizumab or brodalumab)	No prior use allowed
Alefacept, briakinumab, efalizumab, ustekinumab	24 weeks
Biological immunomodulating agents other than above (e.g., adalimumab, infliximab, etanercept)	12 weeks
Other systemic immunomodulating treatments  [e.g., MTX, cyclosporine A, corticosteroids (oral, i.v., transdermal)  , cyclophosphamide]	4 weeks
Other systemic psoriasis treatments (e.g., retinoid, fumarates)	4 weeks
Photo chemotherapy (e.g., PUVA)	4 weeks
Phototherapy (e.g., UVA, UVB)	2 weeks
Medicated psoriasis shampoo (including OTC)	2 weeks
Topical treatment that is likely to impact signs and symptoms of psoriasis (e.g., vitamin D analogues, pimecrolimus, retinoids, salicylvaseline, salicylic acid, lactic acid, tacrolimus, tar, urea, $\alpha$ -hydroxy or fruit acids)	2 weeks
Topical Corticosteroids (TCS) any potency on areas of psoriasis	2 weeks
Live virus vaccines	6 weeks
An investigational treatment or participation in any interventional trial	4 weeks or 5 half-lives (whichever is longer)
Any other treatment known to worsen psoriasis (e.g., beta- blockers, calcium channel blockers)	Stable dose for at least 4 weeks prior to randomization
Cholesterol-lowering medication (e.g., statins)	Stable dose for ≥90 days prior to randomization and remain stable for duration of the study

Concomitant Therapy with TCS (after Visit 2/Baseline)		
Topical Corticosteroids (TCS)	Concomitant Use	
TCS on areas of psoriasis (including scalp)	Hydrocortisone 2.5% cream is allowed on face and intertriginous areas; medicated OTC shampoos are allowed for the scalp	
TCS mild to moderate potency used for up to 7 consecutive days per event for an indication other than psoriasis and on areas not affected by psoriasis	Allowed during the study	

 If the prohibited treatment was used during the study for any indication, the patient must discontinue use of the prohibited treatment if he/she wishes to continue in the study.

 In case of undue safety risk for the patient as determined by the investigator, the patient should discontinue study treatment. If the patient receives a live virus vaccination during the study, the patient must discontinue study treatment.

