### 5.6.2 Discontinuation of study treatment

Discontinuation of study treatment for a patient occurs when study treatment is stopped earlier than the protocol planned duration, and can be initiated by either the patient or the investigator.

Patients may voluntarily discontinue study treatment for any reason at any time.

The investigator must discontinue study treatment for a given patient if, on balance, he/she believes that continuation would negatively impact the risk/benefit of trial participation.

Study treatment must be discontinued under the following circumstances:

- Patient decision
- Pregnancy (see Section 6.7.5 and Section 7.4)
- AEs that in the judgment of the investigator/qualified site staff, taking into account the patient's overall status prevent the patient from continuing study treatment
- Any laboratory abnormalities that in the judgment of the investigator, taking into consideration the patient's overall status, prevents the patient from continuing participation in the study
- Ongoing use of prohibited treatment, use of a prohibited treatment that results in an undue safety risk for the patient as per the investigator's clinical judgment, or receipt of a live virus vaccine during the study (as detailed in Section 5.5.8)
- Any situation in which study participation might result in a safety risk to the patient
- Emergency unblinding

[figure not shown]
The investigator/site staff must contact the IRT to register the patient's discontinuation from study treatment.

If study drug discontinuation occurs because treatment code has been broken, please refer to Section 5.5.9.

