2.5.3 Handling of missing values/censoring/discontinuations

For the primary efficacy variable K16 expression to the treatment at Week 12 (and other time points), a patient with a missing assessment will be considered as having a positive ("yes") response regardless of the reason for missing data (e.g., premature study discontinuation, missed visit, administrative issues). Patients who discontinue the trial for any reason will be considered as having a positive ("yes") response from the time they drop out through Week 52.

For the primary efficacy variable PASI90 response at Week 12 (and other time points), a patient with a missing assessment will be considered as a non-responder regardless to the reason for missing data (e.g., premature study discontinuation, missed visit, administrative issues). Patients who discontinuethe trial for any reason will be considered non-responders from the time they drop out through Week 52.

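### SAP 2.5.3 does not say how PASI 90 and K16 are scored after a prohibited psoriasis treatment was taken and then stopped

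*SAP*

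**What the plan says.** **Prohibition.** Protocol 5.5.8 bans the treatments in Table 5-2 once study treatment has started, giving as its reason that "the use of these treatments could confound the efficacy of the study drug". If one is used anyway, "the patient must discontinue use of the prohibited treatment if he/she wishes to continue in the study". Protocol 5.6.2 requires study treatment to stop only for "Ongoing use of prohibited treatment, use of a prohibited treatment that results in an undue safety risk for the patient", or after a live virus vaccine. A patient who took a prohibited treatment and then stopped it may therefore remain in the study.

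**Intervals.** Protocol Table 5-2 requires time off these agents before randomization: 2 weeks for phototherapy and topical treatments, 4 weeks for other systemic agents and PUVA, 12 weeks for most other biologics, and 24 weeks for the row "Alefacept, briakinumab, efalizumab, ustekinumab". For IL-17 agents it gives no interval, because no earlier use is allowed. The table also permits some topical use after baseline.

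**Analysis sets.** SAP Table 5-1 gives COMD01 (use of "prohibited treatment at any time during the study after randomization") code 0, defined as "INCLUDE IN EVERYTHING".

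**Scoring.** For PASI 90, SAP 2.5.3 says that "a patient with a missing assessment will be considered as a non-responder regardless to the reason for missing data", and it treats patients who leave the trial the same way through Week 52. For K16 it has the same two triggers but imputes *yes*. SAP 2.5.2 reports the percentage with a K16 *no*, so *yes* is the unfavourable category there. Protocol 9.4.3 names missing assessments only. The PASI 90 definition (Protocol 6.6.5, SAP 2.5.1.1) sets no condition on other treatment.

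**The concern.** PASI 90 compares a later score with baseline. The plan keeps other psoriasis drugs away from the baseline score through the Table 5-2 intervals, but has no matching rule for the Week 12 or Week 52 score. A placebo patient who received a biologic in the double-blind period, stopped it and stayed in the study can be a Week 12 success. A patient who left the trial is a PASI 90 failure whatever the reason.

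At stake is what the primary response rates describe. They are meant to compare secukinumab with placebo, and part of the response could come from a third drug. At Week 52 every continuing patient is on secukinumab, so no control arm would reveal it. The analyses in SAP 2.5.4 are logistic models with weight stratum and the same imputation. There is no per-protocol set, so no planned analysis shows how much the result depends on such patients.

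**Working it through.** **1. The plan's own precision figure.** Protocol 9.8 plans 50 secukinumab and 25 placebo patients and tabulates the half-width of a two-sided 95% interval. All ten entries reproduce with

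half-width = 1.96 × √[p(1 − p)(1/n₁ + 1/n₂)] + (1/n₁ + 1/n₂)/2.

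At p = 50% and 50 vs 25: 1.96 × √(0.25 × 0.06) + 0.03 = 0.240 + 0.030 = 27.0%. At 30% or 70%: 0.220 + 0.030 = 25.0%. The planned margin is therefore 25 to 27 points.

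**2. Which use falls inside a Table 5-2 interval.** Subtract the interval from the assessment week. The intervals are written for the time before randomization and are applied here by analogy.

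| Interval | Last use that reaches Week 12 | Last use that reaches Week 52 |
|---|---|---|
| 2 weeks | Week 10 or later | Week 50 or later |
| 4 weeks | Week 8 or later | Week 48 or later |
| 12 weeks | any time in the double-blind period | Week 40 or later |
| 24 weeks | any time in the double-blind period | Week 28 or later |

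**3. Weight of one patient at Week 12.** Placebo: 1/25 = 4 points. Secukinumab: 1/50 = 2 points. The same weights apply to both primary variables.

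**4. Background PASI 90 rates.** Pooling Protocol Table 3-1:

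- Secukinumab 300 mg: (145 + 175 + 35 + 33)/(245 + 327 + 59 + 60) = 388/691 = 56.2%.
- Placebo: (3 + 5 + 0 + 0)/(248 + 326 + 59 + 61) = 8/694 = 1.2%. That is 25 × 0.0115 = 0.29 expected responders among 25.

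**5. Illustration.** The documents give no frequency of prohibited use, so the counts below are assumptions. Start from 28/50 (56%) and 0/25, with the unpooled interval d ± 1.96 × √[p₁(1 − p₁)/50 + p₂(1 − p₂)/25].

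| Scenario | Difference (95% CI) |
|---|---|
| 28/50 vs 0/25 | 56.0% (42.2 to 69.8) |
| 1 placebo patient left as responder | 52.0% (36.2 to 67.8) |
| 2 placebo patients | 48.0% (30.6 to 65.4) |
| 3 placebo patients | 44.0% (25.2 to 62.8) |
| 1 of the 28 secukinumab responders rescored as failure | 54.0% (40.2 to 67.8) |
| 3 of the 28 rescored | 50.0% (36.1 to 63.9) |
| 5 of the 28 rescored | 46.0% (32.2 to 59.8) |

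With 0/25 on placebo this interval takes no variance from that arm, so it is too narrow in those rows. The shifts in the point estimate do not depend on that.

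**The case against.** The best defence is that scoring what is observed, whatever else was taken, is a legitimate treatment-policy choice. The study is exploratory and tests no formal hypothesis. Deviations are tabulated by arm (SAP 2.3.1) and concomitant medications are summarised by arm (SAP 2.4.2), so a reader could see that such use occurred. One placebo patient moves the estimate 4 points against a planned margin of 25 to 27. All of this limits the weight of the point. It does not settle it: neither document declares a treatment-policy approach, the protocol's stated reason for the ban points the other way, and the tabulations do not show the effect on response.

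Four stronger readings are tempting, and the documents do not support them.

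- *That code 0 for COMD01 is itself an error.* It governs set membership only. Keeping the patient in the Full Analysis Set fits the stated intent-to-treat principle. The gap is in SAP 2.5.3.
- *That the plan counts any switch of therapy as success.* Ongoing use requires study treatment to stop. Protocol 5.6.2.1 then calls for an end-of-treatment visit and a recorded reason for premature study discontinuation, and SAP 2.5.3 scores patients who leave the trial as PASI 90 failures. What remains is use that stopped while the patient stayed.
- *That the bias always works against secukinumab.* Use in the secukinumab arm inflates the difference.
- *That the Week 52 rate is inflated by a calculable amount.* Assuming 5 to 10% of patients affected and multiplying by 56% gives 2.8 to 5.6 points. But the frequency has no source, the 56% is a Week 12 rate, and the product equals inflation only if none of those patients would have responded on secukinumab alone.

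**Conclusion.** The point holds as a gap in SAP 2.5.3. A patient who took a prohibited psoriasis treatment after randomization, stopped it and stayed in the study is scored on the observed PASI 90 and K16 result. The protocol itself says that such use could confound efficacy. This follows from silence, not from a stated rule.

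The size at Week 12 is 4 points of dilution per affected placebo patient and 2 points of inflation per affected secukinumab patient. Affected here means scored a success only because of the other drug. The total depends on a frequency that the documents do not give. No figure can be put on Week 52.

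Two limits apply. The protocol does not say that Table 5-2 measures how long a drug affects the skin; using its intervals after randomization is an analogy, chosen because they are the plan's own. And the definition of K16 response is not visible in the documents, so the K16 part rests on the SAP's coding alone. This is a cheap improvement worth making, not a flaw that undermines the trial.

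**What to change.** Keep these patients in the Full Analysis Set and add a scoring rule to SAP 2.5.3 for both primary variables:

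- An assessment is scored in the unfavourable category if it was made after the start of a treatment that Table 5-2 prohibits for its effect on psoriasis, and before the Table 5-2 interval for that treatment has elapsed since last use.
- The unfavourable category is non-responder for PASI 90. For K16 it is the category the SAP already uses for missing data (*yes*). The word non-response should not be used for K16, because under the SAP's coding it could be read as the favourable *no*.
- For agents with no stated interval (IL-17 agents), all later assessments are scored this way.
- Topical use that Table 5-2 permits after baseline does not trigger the rule.
- The as-observed (treatment-policy) result is reported alongside as a sensitivity analysis.

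The cost is a short SAP text and a derived flag. Protocol 5.5.8 already requires prohibited treatments to be entered on the eCRF, so no new data are needed. The downside is slightly lower response rates, with some patients who would have responded anyway scored as failures; the as-observed analysis shows how much that matters. The change concerns analysis only and leaves clinical management as it is.
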